4. STUDY DESIGN

4.1 General Design

This is a randomized controlled trial to test the effects on long-term weight loss of a novel stigma-reduction intervention combined with standard BWL treatment, as compared to BWL alone. Participants will be a total of 104 men and women seeking weight loss, ages 18 years and older, with a body mass index (BMI) of 30 kg/m² or above (or 27 kg/m² or above with an obesity-related comorbidity), a history of experiencing weight bias, and elevated levels of WBI. Participants will attend a screening visit in which they will complete a behavioral evaluation with a psychologist and a medical history that will be reviewed by a nurse practitioner or physician. Questionnaires assessing experiences and internalization of weight bias, with confirmation by interviewer assessment during the behavioral evaluation, will be used to determine whether participants meet criteria for having high levels of WBI. Eligible consenting participants will be randomly assigned to the standard BWL intervention (n = 52) or the stigma + BWL intervention (n = 52). All participants will attend weekly, 90-minute group meetings for 20 weeks (20 visits). In the stigma + BWL treatment group, beginning at week 5, 60 minutes will be devoted to BWL and 30 minutes to weight stigma. In the standard BWL treatment group, the additional 30 minutes will be devoted to sharing recipes and food preparation tips. Following 20 weeks of weight loss treatment, participants will attend group meetings focused on weight loss maintenance, monthly from weeks 21-46 (6 visits), and every-other-month from weeks 47-72 (3 visits). Maintenance sessions in the stigma + BWL group will continue to incorporate discussion of WBI and stigma-related barriers to physical activity. Assessments – which include questionnaires, blood draws, and measurements of body weight and physical activity – will occur at baseline and weeks 20, 46 (no blood draw this week), and 72. Weight will be measured at every group meeting for clinical purposes.

Other Therapy:

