6.2 Study Visits

Screening visit. The following procedures will be completed at the screening visit as discussed above: informed consent, medical history, weight, height, and meeting with psychologist whose assessment will be used as a part of determining the subject's eligibility for the study. This medical history will be reviewed by the study physician or nurse practitioner to determine whether there are any contraindications to weight loss. These contraindications include but are not limited to: any major active kidney, liver, cardiovascular, or cerebrovascular disease; type 2 diabetes; or the use of any medications that significantly affect weight (weight loss or weight gain, including steroids). Female participants will be ineligible for the study if they are pregnant or nursing. Applicants with a history of cardiac events or other significant CVD risk factors may also be asked to supply a letter from their primary care physician providing medical clearance for them to participate in this study. Applicants will be required to monitor their food intake following the screening visit and return their food records before being provisionally accepted into the study.

Randomization visit. Within one month of the start of the group intervention, participants will attend a visit in which their weight and blood pressure will be measured and, if they still meet all study criteria, they will be randomized to their treatment group. Accelerometers will be given to participants to monitor their activity for 7-10 days. Participants will return their accelerometers in person, at which time their activity for the past week will be assessed with a structured interview. Participants may be held financially responsible if the accelerometer is lost, stolen, or not returned.

If a participant is randomized but no longer able to attend groups as scheduled, it may be available to them to begin the group intervention, in the same treatment condition as assigned at randomization, in a subsequent cohort. In this case, baseline measurements will be repeated within one month of the start of treatment.

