BWL intervention. Participants in this group will be provided with 20 weekly BWL sessions, based on the Diabetes Prevention Program (DPP) manual,⁵⁹ followed by 6 monthly weight loss maintenance sessions and 3 every-other-month sessions (for a total of 29 visits over 72 weeks). A diet of 1200-1499 calories per day will be prescribed for participants < 250 lb, and 1500-1800 for those ≥ 250 lb.^{59,60} Participants will be instructed to eat a balanced deficit diet with approximately 15-20% of kcal from protein, 20-35% from fat (less than 10% from saturated fat), and the remainder from carbohydrates.⁵⁹ Session topics during the first 20 weeks will include self-monitoring, stimulus control, slowing eating, social support, cognitive restructuring, portion sizes, and goal-setting.⁵⁹ Those during weeks 21-72 will focus on continued self-monitoring and skills required for weight loss maintenance and relapse prevention. BWL sessions will last 90 minutes. Beginning at week 5, 60 minutes of the group session will be devoted to BWL content, with an additional 30 minutes devoted to discussing recipes and food preparation.

Physical activity will be prescribed at a level consistent with data showing that ≥ 250 min/wk is associated with improved long-term weight loss.^{12-14,61} Activity will begin at week 2 with 60 min/wk, and will gradually progress by 10 minutes over 2-4 week intervals until achieving 150 min/wk by week 20, 200 min/wk by week 46, and 250 min/wk by week 72. Participants will be instructed to spread the 150-250 minute doses of activity equally across at least 5 days, and to accumulate their structured physical activity in bouts that are ≥ 10 minutes in duration. Moderate intensity will be prescribed with an emphasis on walking; the vast majority of our research participants self-select this form of activity.

Participants who cannot attend any given group session will be offered a brief (10-20 minute) make-up session (in person or by phone) during the week with the group leader or a study staff member. Participants may also meet briefly with the group leader individually, outside of group sessions, up to 3 times during the initial 20-week study period if they have not lost at least 1% of their body weight by week 4, report difficulty controlling their eating, or describe other challenges preventing them from adhering to the program that cannot be fully covered during group sessions.

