Stigma + BWL intervention. Participants in this group will receive the same BWL program described above, which will be combined with a stigma-reduction intervention. Beginning at week 5, the 60-minute BWL sessions will be followed by 30 minutes devoted to stigma-related content. Session topics will be based on those tested in a previous pilot study, including: psychoeducation about weight and weight stigma; challenging myths and cognitive distortions related to weight; strategies for coping with instances of stigma; and increasing empowerment and body esteem. The effects of weight stigma on health behaviors will be discussed, and sessions will focus specifically on helping participants overcome stigma-related barriers to physical activity. For example, they will be given strategies to cope with anticipated stigma while exercising in public spaces (e.g., while walking), as well as to challenge self-critical beliefs (e.g., that they are lazy) which may otherwise lead them to avoid exercising. These concrete strategies, along with reducing WBI and improving self-confidence, are intended to increase participants' self-efficacy for and engagement in physical activity. In the monthly and every-other-month weight loss maintenance sessions from weeks 21-72, strategies for coping with weight stigma and challenging internalized beliefs will be reviewed, and participants will be encouraged to use these strategies specifically with physical activity.

As with the BWL Intervention, participants who cannot attend group sessions or are experiencing difficulties adhering to the program will be eligible for brief individual meetings with the group leader or study staff (as described above).

Adjustments to treatment sessions due to COVID-19. During the pandemic, all group sessions will be conducted virtually on the platform BlueJeans. Group members who do not have access to video technology will be invited to join the meeting by phone. Makeup sessions will continue to be offered by phone. Treatment session handouts will be sent to participants by email. Since weight will no longer be measured in person at group meetings, all participants will be sent an EatSmart Precision Digital Scale. Prior to group meetings, participants will be asked to email the study coordinator their weight. This will allow the group leader and study team to continue to monitor participant weight loss for clinical purposes.

Outcome assessment visits

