7. STATISTICAL ANALYSIS

Sample size calculation

Using a sample size equation for longitudinal clustered samples,⁸⁴ a power analysis was conducted for the **primary outcome: percent weight change at week 72**. Estimated group means, attrition rate, intraclass correlation (ICC), and variances were derived from data from prior studies

conducted at our Center.⁷² Specifically, we predict a 72-week weight loss of 9% in the stigma + BWL group and 5% in the BWL group, with expected standard deviations of 7%.⁷² Based on these estimates, a baseline sample size of 104 participants (52 per group), assuming a 20% attrition rate, an ICC of .80, and 4 assessment points, will give us 80% power to detect a between-treatment group difference at week 72 of 4% (effect size: 0.57) to be significant at alpha = 0.05. The power analysis was conducted using PASS v14. All secondary outcomes will be considered exploratory and will provide valuable findings that will help to inform larger studies. This study has not been powered to detect differences in changes in physical activity, cardiometabolic outcomes, or psychosocial variables.

Analysis plan

Data quality and integrity will be checked by assessing the data for missing and out-of-range values with basic statistical procedures, including univariate statistics and visual graphical displays (e.g., scatter plots). We will investigate all questions of data quality and integrity prior to performing any statistical modeling. To test the adequacy of randomization, preliminary analyses will include a comparison of all participant demographic and baseline characteristics by randomized treatment groups (t-tests or Wilcoxon rank sum tests for continuous variables and Chi-Square test or Fisher's Exact test for categorical data). If imbalances are observed, the relevant variables will be included as covariates in the final analyses.

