All data will be analyzed with a modified intention-to-treat principle. Participants who attend at least one group meeting (i.e., receive a dose of treatment) will be included in the analyses; participants who do not attend a single group meeting will not be included in the analyses. Analyses will be two-tailed with a significance level of 0.05, and will be conducted using SPSS version 24.0 or SAS version 9.4. To assess the primary outcome of percent weight change by treatment group, a mixed effects model will be fit with Treatment Group (*stigma+BWL, BWL*) as a between subjects factor and Time (*Weeks 20, 46, 72*) as a categorical within-subjects factor. We will use the group x time interactions with the time main effect to estimate and test treatment group differences at each time point, with the 72-week time point as our primary test. In fitting a mixed effects model with residual maximum likelihood (REML), a variance-covariance structure must be selected. The criteria for selecting the best form of the variance-covariance structure will be based on criteria such as the Akaike's Information Criterion (AIC). We will include as baseline covariates any variables that differ significantly between the treatment groups at baseline and show significant relationships with the outcome. The results from the mixed model will be summarized by mean(SE) for each treatment group at each time point. Residual analyses will be conducted to check for outliers and influential points and violations in the normality assumption. If violations are detected, variance-stabilizing transformations will be considered. Logistic regression will be used to test for between-group differences in categorical weight loss ($\geq 5\%$ and $\geq 10\%$ of initial body weight) at weeks 72, 46, and 20.

The second aim of assessing changes in physical activity and self-efficacy, and the secondary aims of comparing changes in cardiometabolic risk factors and psychological well-being (including WBI), will be analyzed using the same methods as described above for the mixed effects model used for the primary aim. Changes in all outcomes will be summarized by mean(SE) for each treatment group at each time point. Logistic regression will be used to test for between-group

differences at weeks 20, 46, and 72 in the percentage of participants who have remitted from elevated WBI, as indicated by no longer having a score of 4 or above.

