This study will consider death, pregnancy, bariatric surgery, amputation, and other major medical events or procedures that require a participant to terminate treatment as "censoring events." For primary analyses, participants experiencing these events will be censored at the last measured weight before the event occurred. As discussed above, the primary analysis techniques being employed (i.e., linear mixed models) can accommodate incomplete participant response profiles, so these participants will still be included in the analyses. Additional sensitivity analyses may be conducted in which data will be censored due to other factors that directly affect weight (e.g., change of medication that affects weight, receipt of additional weight-related treatment, change in smoking status, or other major medical changes that occur within 3 months of an assessment visit).

Additional analyses may be conducted to explore potential effects of cohort, time of group meeting, and group leader on weight loss and changes in WBI. Analyses may also explore potential differences in attendance between groups and the effects of attendance on weight loss and changes in WBI.

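### The primary week-72 test makes no allowance for correlation within arm-specific meeting groups, and the only analysis that could show its effect is optional

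*Combined protocol and SAP*

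**What the plan says.** All references are to the combined protocol and SAP.

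- **Delivery.** Section 4.1 randomizes individuals, 52 per arm, and treats everyone in groups: "All participants will attend weekly, 90-minute group meetings for 20 weeks (20 visits". Six monthly and three every-other-month group sessions follow, up to week 72.
- **Arm-specific content.** Under Section 6.2, from week 5 the BWL arm has 60 minutes of BWL content "with an additional 30 minutes devoted to discussing recipes and food preparation". In the stigma + BWL arm, "the 60-minute BWL sessions will be followed by 30 minutes devoted to stigma-related content". A randomized participant who cannot attend as scheduled may be deferred: "it may be available to them to begin the group intervention, in the same treatment condition as assigned at randomization, in a subsequent cohort".
- **Primary model.** In Section 7, Analysis plan, "a mixed effects model will be fit with Treatment Group" and Time as factors, and their interaction gives the treatment difference at each visit, "with the 72-week time point as our primary test". AIC guides the choice of variance-covariance structure. Baseline covariates enter only where the arms differ. No meeting-group, cohort or leader term is listed.
- **Sample size.** Section 7 arrives at 104 participants "assuming a 20% attrition rate, an ICC of .80, and 4 assessment points".
- **Group effects.** They appear once, at the end of Section 7: "Additional analyses may be conducted to explore potential effects of cohort, time of group meeting, and group leader on weight loss", and on changes in WBI.

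**The concern.** People who sit in the same group share a leader, a meeting time and each other's company for up to 29 sessions. If that makes their week-72 outcomes alike, and each group belongs to one arm, part of the difference between arms is a difference between a handful of groups. A model that treats participants as independent counts this as person-level noise averaged over about 40 people per arm, so its standard error is too small.

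This is the trial's single primary test. A significant result could then partly reflect a few groups that did well, and nothing the plan commits to would let a reader tell. An analysis that may or may not be run, and whose form is not specified, does not settle the matter afterwards.

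**Working it through.** **Step 1. What the ICC of .80 covers.** Inputs from Section 7: difference 4 points, SD 7, two-sided alpha 0.05, power 80%, ICC .80, 4 assessments, 20% attrition.

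- Plain two-sample size: 2 × (1.96 + 0.842)² × 7² / 4² = 48.07 per arm.
- Repeated-measures factor with .80 as the correlation within a person: (1 + 3 × 0.80)/4 = 0.85.
- 48.07 × 0.85 = 40.9, so 41 per arm; 41/0.80 = 51.25, so 52 per arm and 104 in total.

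This is the plan's figure exactly. Read as a meeting-group ICC with, say, 10 completers per group, .80 would give a design effect of 1 + 9 × 0.80 = 8.2 and 48.07 × 8.2 = 394 per arm. So .80 is the within-person correlation, and the sample size holds no allowance for meeting groups.

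**Step 2. Are groups arm-specific?** No single sentence says so. But one session cannot give its last 30 minutes to both recipes and stigma content, and a deferred participant must join the same condition in a later cohort. The inference is strong. It is weakest for weeks 1-4, where no arm-specific content is described.

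**Step 3. Type I error if groups are ignored.** With m completers per group and arm-specific ICC ρ, the variance of the contrast is multiplied by DE = 1 + (m − 1)ρ, and the actual two-sided error is about 2 × [1 − Φ(1.96/√DE)]. Expected completers are 52 × 0.8 = 41.6 per arm. The splits below and all values of ρ are assumptions. Example, 4 groups of 10 at ρ = 0.02: DE = 1 + 9 × 0.02 = 1.18, 1.96/√1.18 = 1.804, error 7.1%.

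| Groups × completers per arm | DE at ρ = 0.01 / 0.02 / 0.05 | Error by formula (%) | Error by simulation (%) |
|---|---|---|---|
| 8 × 5 | 1.04 / 1.08 / 1.20 | 5.5 / 5.9 / 7.4 | 5.4 / 5.9 / 7.7 |
| 4 × 10 | 1.09 / 1.18 / 1.45 | 6.0 / 7.1 / 10.4 | 6.1 / 7.0 / 10.3 |
| 3 × 13 | 1.12 / 1.24 / 1.60 | 6.4 / 7.8 / 12.1 | 6.5 / 8.0 / 12.1 |

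At ρ = 0 the error is 5%. The simulations use week 72 alone, with equal groups. In the same setting, comparing group means with between-group degrees of freedom holds the error at about 5%.

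**Step 4. Variance shared by both arms of a cohort.** Such variance cancels in the treatment difference. With 4 groups of 10 per arm and a total ICC of 0.05, simulated error is about 4.7% if all of it is shared and 5.7% if 0.04 of it is shared. Only the arm-specific part inflates the error.

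**Step 5. Power if the group-level model became the primary test.**

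- Completers only: SE = 7 × √(2/41.6) = 1.535; 4/1.535 = 2.606; power = Φ(2.606 − 1.96) = 74.1%.
- Upper limit, if every dropout supplied weeks 20 and 46 at correlation .80: R² = 2 × 0.64/1.8 = 0.711; variance per arm = 49 × (0.289/41.6 + 0.711/52) = 1.010; SE = √(2 × 1.010) = 1.42; power 80.3%.
- Four groups per arm leave 6 between-group df, with critical value 2.447. On the completer basis, the noncentral t distribution gives power of 58.8% at ρ = 0. With DE = 1 + 9.4ρ (10.4 completers per group), it is 55.1%, 51.8% and 43.9% at ρ = 0.01, 0.02 and 0.05.

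**The case against.** The strongest reply is that nothing in the documents shows a problem of any size. They give no group ICC, and a low one is plausible: only nine group sessions fall between week 20 and the week-72 test, and missed sessions are made up individually. With many small groups and ICC 0.01 the excess is under half a point. Against that, moving the primary test to group level costs about 15 points of power in the four-group case even if the ICC is zero. All of this stands, and it is why the change proposed here does not replace the primary test.

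Two stronger readings are tempting, and the documents support neither. A reader might infer that the trial's type I error is inflated; the plan shows only that the primary test is unprotected if arm-specific correlation exists. A reader might also infer that any similarity among members of a group is harmful, including similarity caused by season or the pandemic move to virtual sessions. Where such influences act equally on both arms of a cohort, they do not inflate the error (step 4).

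One reply does not stand. Section 7 describes its sample-size equation as one for clustered longitudinal data, which might suggest that groups are covered. Step 1 shows that the clusters are the repeated measurements of one person.

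The secondary models and logistic regressions have the same gap, but Section 7 declares secondary outcomes exploratory, so they matter less.

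**Conclusion.** The point holds as a conditional one. The primary model omits meeting group, the sample size does not allow for it, and the only related analysis is optional. If week-72 weight change correlates within an arm's groups beyond any shared cohort effect, the 5% test is anti-conservative, by roughly half a point to seven points over the assumed range (5.4% to 12.1% for ICC 0.01 to 0.05).

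This rests on groups being arm-specific, which is inferred from session content, and on assumed group numbers, sizes and ICCs. It does not establish that material inflation will occur. It does mean that, as planned, a positive primary result could not be separated from a few good groups.

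**What to change.** In Section 7, change *may* to *will* for one prespecified analysis of the primary week-72 contrast that allows for the meeting group first attended. The modified intention-to-treat set requires at least one meeting, so every analysed participant has such a group.

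- Use either a random group effect at week 72 or a comparison of group means, with between-group degrees of freedom. A single group intercept common to all visits is less safe: at ICC 0.05 it gave 5.6-5.8% in simulation when the group effect grew towards week 72 or was only half-correlated over time.
- Do not revert to person-level degrees of freedom when the group variance is estimated as zero. With 4 groups of 10 per arm, that rule made the test conservative (3.0-4.5%) with no gain in power (56.1% against 57.2% at ICC 0).
- Report the number and size of groups and the estimated group ICC, and state that a positive primary result will be interpreted in the light of this analysis.

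The cost is some SAP wording and a little more analysis; the planned exploration of cohort, meeting time and leader implies that the identifiers will be held. With few groups the group-level result will be imprecise, and it errs on the conservative side if the correlation is mostly shared by both arms. The primary test itself stays unadjusted.

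The stronger option is to make this model the primary test. That protects the error rate, but with 4 groups per arm completer-based power at ICC 0 falls from about 74% (up to about 80% if partial profiles are recovered) to about 59%. The sponsor should make that choice openly, with the planned number of groups stated. Group-level versions of the exploratory secondary and logistic models are optional.
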